10.0 Local Number of Participants

10.1 Local Number of Participants to be Consented: Based on recruitment in previous studies in this population performed by our lab, we expect that about 75% of our sample of children with UCP will reside in the state of Minnesota. The remaining 4 participants will be recruited from the greater Midwestern and Western regions. We expect to enroll all CTD from the greater Twin Cities Metropolitan area. The maximum number of enrolled participants is 40 children with UCP and 10 CTD.

11.0 Local Recruitment Methods

11.1 Recruitment Process: Recruitment will take place immediately after approval and continue, at the latest, through the 24th month of the study. We expect most participants will be recruited from the state of Minnesota. Based on our previous recruitment data, approximately 25% will reside in other states.

We will use established databases from our previous work, totaling nearly 400 children with UCP who, barring changes in medical status, meet the proposed study criteria. In addition, we will recruit using the following sources/methods: other existing databases, newspaper advertisements, television/radio programs, webpages (the Children's Hemiplegia and Stroke Association ([chasa.org](http://www.chasa.org)), HemiKids website (<http://www.hemikids.org/>),

ResearchMatch.com), social media, and clinician contact postings We have experienced exceptional participation (increase in overall enrollment in our studies from 9% to 14% over the last 5 years), retention (100% in 3 studies of 50 total children), and adherence (99.8%) in our trials of over 539 total visits.

Source of Participants: With IRB approval, we will screen children for research recruitment through physician-based referrals. This has been our most effective recruitment tool to date (>57% of referrals) and will allow expansion of our current database. Additional sources are the local, state, and national communities that respond to advertisements and postings on websites described in Section 12.1

- 11.2 Identification of Potential Participants: All interested caregivers/participants will be screened on the telephone by the study coordinator or an authorized member of the research team to determine if the child meets the inclusion/exclusion criteria using IRB-approved pre-screening forms (Appendix A). Following telephone screen, we will send the caregiver/participant a medical record release form that grants release of their child's medical records to further determine eligibility (Appendix B and C). When we receive this signed form, we will submit it to the appropriate hospital/clinic. The medical director will review the medical records for appropriate inclusion.
- 11.3 Recruitment Materials: We will use emails (Appendix H) and printed flyers (Appendix I) to advertise this study.
- 11.4 Payment: Participants will be paid \$50 in the form of a debit card after completing the study. The Greenphire ClinCard will be used for payments. Payment will be made using a pre-paid debit card called Greenphire ClinCard. It works like a bank debit card. We will give you a debit card and each time you receive a payment for participation in this study, the money will be added to the card after each completed visit.

You may use this card at any store that accepts MasterCard or you can use a bank machine to remove cash. However, there may be fees drawn against the balance of the card for cash withdrawals (ATM use) and inactivity (no use for 3 months). We will give you the ClinCard Frequently Asked Questions information sheet that answers common questions about the debit card. You will also receive letters with additional information on how you can use this card and who to call if you have any questions. Be sure to read these letters, including the cardholder agreement, for details about fees.

The debit card system is administered by an outside company. The company, Greenphire, will be given your name. They will use this information only as part of the payment system. Your information will not be used for any other purposes and will not be given or sold to any other company. Greenphire will not receive any information about your health status or the study in which you are participating.

Any demographic information collected and provided to Greenphire is stored in a secure fashion and will be kept confidential, except as required by law.

Payment you receive as compensation for participation in research is considered taxable income. If payment to an individual exceeds \$600 in any one calendar year, the University of Minnesota is required to report this information to the Internal Revenue Service (IRS). Research payments to study participants exceeding \$600.00 during any calendar year will result in a FORM 1099 (Miscellaneous Income) being issued to you and a copy sent to the IRS.

At the end of the study, you will be provided with information regarding how your hand movements changed before and after the intervention. This information is not intended to have clinical significance.

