5.0 Procedures Involved

5.1 Study Design: This is a randomized, sham-controlled, double-blinded study. The intervention consists of a single, 20 minute session of tDCS paired with motor training (see Figure 2). Participants will be randomized to either real or sham tDCS. The participants and the members of the research team involved in assessments and testing will be blinded to intervention group (real or sham tDCS), but the other research staff/PI/Co-Is will be unblinded.

5.2 Study Procedures:

Pre-study

[figure not shown]

Figure 2. Pre-study timeline and study design.

Participant Screening and Enrollment

Participants will be initially screened for inclusion and exclusion criteria during a phone interview (Appendix A). Initial consent will be obtained over the phone to allow the caregiver to disclose protected health information (PHI) about his/her child. If the family is interested following this phone screen, we will obtain HIPAA consent to perform a medical record review (Appendix B and C). A review is then completed by the study medical director for review of inclusion/exclusion by history and MRI/CT radiographic reports of the brain (Appendix D). Eligibility will be verified by the principal investigator after this review. Eligibility is then discussed with the legal guardian and a formal schedule is established. A pre-study letter will then be sent (Appendix E). Informed consent/assent will be completed before on the day of the MRI acquisition.

The research team will utilize the CMRR Center's screening tools and adhere to the screening SOP during enrollment of all research participants in this protocol. The CMRR Center's screening tools and SOP are IRB approved under the CMRR Center Grant (HSC# 1406M51205) and information regarding screening procedures is publically available on the CMRR website.

Randomization

Participants will be randomly assigned to receive real or sham tDCS. Children with presence of a lesioned hemisphere MEP response may receive 1) ipsilesional anodal; 2) contralesional cathodal tDCS or 3) sham tDCS. Children without a lesioned hemisphere MEP may receive 1) contralesional anodal or 2) sham tDCS. Participants and their families will be blinded to group assignment. Participants will be unblinded after completing the study.

Magnetic Resonance Imaging (MRI) Acquisition

Location: Center for Magnetic Resonance Research (CMRR)

Time: 1 hour (including preparatory time)

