After the first 2 minutes of stimulation, the participant is questioned about pain at the electrode sites. If the stimulation is painful, a small amount of additional saline (2-4 mL) is added to the sponge, taking care to avoid wetting adjacent hair and thereby increasing the electrode area, and the tightness and placement of the band are checked. If pain persists, the stimulation intensity is decreased, and symptoms re-assessed. If pain still persists, stimulation is stopped and the electrode sites are checked. This procedure is repeated twice (every 5 minutes during tDCS) with saline solution (2-4 mL) added as needed.

Participants will receive a total of 20 minutes of active or sham tDCS. During stimulation, participants will practice the novel reaching task described above at a comfortable pace. No conversations between participant and researchers or caregivers will be allowed, except those that pertain to safety.

Post-intervention Assessments

Immediately following the intervention, TMS and Behavioral assessments will be performed at 0, 15, 30, and 60 minutes following the intervention (see Figure 2).

Other Procedures

Computational Modeling

Computational modeling of electric fields produced by tDCS will be performed using SimNIBS (Simulation of Non-invasive Brain Stimulation). Using T1-anatomical images, individual skull and brain anatomy will be reconstructed, and electric fields computed using a finite element method. The primary outcome is the estimated peak electric field strength for the M1-SO montage.

Safety Monitoring

We will use questionnaires (Appendix F) to document symptoms associated with non-invasive brain stimulation before and after the intervention and testing session. This tool asks participants about the presence and severity of symptoms such as tingling, itchiness, and headache. We will also measure heart rate and blood pressure before and after the procedures.

Follow-Up: A member of the research team will contact each participant and their caregivers within one week of completing the study to check for any adverse events. There is no long-term follow-up data collection planned.

- 5.3 Study Duration: Each participant will complete the study in either one day (MRI and intervention, four hours total) or on two separate days (one hour MRI, and three hours intervention). If done on two days, the MRI and intervention will be separated by no longer than a two week (14 day) period.

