7.0 Sharing of Results with Participants

- 7.1 This study is not designed to produce a direct benefit to the participant. We will not share specific individual results with participants and families. At the time of publication of any manuscripts associated with this study, we will send a lay summary and a copy of the article to each participant and their family.

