9.0 Vulnerable Populations

9.1 Vulnerable Populations:

- Children
- Pregnant women/Fetuses/Neonates
- Prisoners

- Adults lacking capacity to consent and/or adults with diminished capacity to consent, including, but not limited to, those with acute medical conditions, psychiatric disorders, neurologic disorders, developmental disorders, and behavioral disorders
- Approached for participation in research during a stressful situation such as emergency room setting, childbirth (labor), etc.
- Disadvantaged in the distribution of social goods and services such as income, housing, or healthcare
- Serious health condition for which there are no satisfactory standard treatments
- Fear of negative consequences for not participating in the research (e.g. institutionalization, deportation, disclosure of stigmatizing behavior)
- Any other circumstance/dynamic that could increase vulnerability to coercion or exploitation that might influence consent to research or decision to continue in research
- Undervalued or disenfranchised social group
- Members of the military
- Non-English speakers
- Those unable to read (illiterate)
- Employees of the researcher
- Students of the researcher
- None of the above

9.2 Additional Safeguards: We are studying children and young adults aged 7-21 with a specific diagnosis of cerebral palsy. As we are a pediatric laboratory with experienced pediatric researchers, clinicians and trainees, comprehensive efforts have been made to ensure that our procedures are developmentally appropriate to both child and family. Recruitment materials, study information, and conversations are tailored to a pediatric population. Participant-specific study materials are provided before participation in interventions and testing sessions, and age-appropriate adaptations for each procedure/test are used. Our team has created videos that help explain the research and procedures to families. These videos can be viewed at any time before enrolling or participating in the study. ([[name] Lab Video](#); [TMS Video](#)). We also have a network of past participant families who have offered to share their experiences in our research studies with potential participants.

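### As worded, section 5.2 lets families learn their arm while other children are still being enrolled, and sections 7.1 and 11.4 contradict each other on whether individual results are shared

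*Combined protocol and SAP*

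**What the plan says.** **Blinding and unblinding.** Section 5.1 describes the trial as sham-controlled and double-blinded. The Randomization paragraph of section 5.2 says: "Participants and their families will be blinded to group assignment". It then says: "Participants will be unblinded after completing the study". It does not tie unblinding to the last participant, to the follow-up call or to any data milestone.

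**Individual results.** Section 7.1 says: "We will not share specific individual results with participants and families". What it offers instead comes at publication: "we will send a lay summary and a copy of the article to each participant and their family". Section 11.4, at the end of the text on payment, says: "At the end of the study, you will be provided with information regarding how your hand movements changed before and after the intervention". It adds: "This information is not intended to have clinical significance".

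**Timing.** Section 5.3 says: "Each participant will complete the study in either one day (MRI and intervention, four hours total) or on two separate days". The same section expects enrolment to take 24 months. The Follow-Up paragraph of 5.2 schedules a call about adverse events within a week of a participant completing the study. Section 17.2 provides for an interim safety analysis once half the participants are enrolled, and adverse events reported in that call are among its inputs.

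**The concern.** In a trial that enrols children one after another, blinding has to last until the final child has been assessed. If arms are released family by family, the number of families who know theirs grows while other children are still to be tested.

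Two things are exposed. The first is later children's expectations. The primary behavioural outcome (time to complete a novel movement task, section 3.1) and the secondary ones (Box and Blocks, grip strength, section 3.2) depend on effort. Symptom questionnaires, also a secondary outcome, depend on what a child expects to feel. The second is the unblinded family's own report in the follow-up call. A family that knows its child had real stimulation may attribute or report symptoms differently from one that knows its child had sham.

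The conflict between 7.1 and 11.4 is a separate fault in the same area. Staff cannot obey both sections. If 11.4 is followed at each child's own end of participation, an individual result goes out alongside the arm.

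**Working it through.** No sample-size, power or alpha figure bears on this point, so the check sets the sections side by side.

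**1. Whose completion does 5.2 mean?** Three other uses point to the individual child:
- Section 5.3 defines completion for each participant, as one day or two separate days.
- The Follow-Up paragraph of 5.2 counts the one-week window for each participant's call from completion.
- Section 11.4 pays each participant after completion.

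The natural reading of the unblinding sentence is therefore also per child.

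**2. How long could early families know their arm while enrolment is open?**
- Longest gap between MRI and intervention (5.3): 14 days.
- Follow-up call (5.2): up to 7 days later.
- Longest span for one child, MRI to call: 14 + 7 = 21 days.
- Enrolment period (5.3): up to 24 months.

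A child enrolled at the start would be finished in about three weeks. If enrolment uses its full period, that family could know its arm for roughly 23 of the 24 months. Section 10.1 caps enrolment at 40 + 10 = 50 children, so all but the last few would finish while others were still to be tested, unless recruitment were bunched at the end.

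**3. Can unblinding come before the child's own call?** The call is timed from completion, so completion comes first. Unblinding is permitted once completion has occurred. Nothing requires the call to be made before the arm is disclosed.

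**4. Do 7.1 and 11.4 conflict?** A child's own change in hand movement from before to after the intervention is a specific individual result. Section 7.1 excludes such results and makes no exception for information without clinical meaning, so the disclaimer in 11.4 does not reconcile them. The conflict exists on either reading of when the study ends.

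**5. Does 11.4 fix the timing?** No. Its phrase can mean the child's last study day or the end of the trial. Only the first would put individual results in circulation during enrolment.

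**6. Is there a safeguard elsewhere?** No section delays release of arms or asks families to keep them confidential.

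**The case against.** The strongest reply is that the path from early release to a biased result is long and only partly documented. Several parts of that reply stand.

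- **Peer contact.** Section 9.2 says: "We also have a network of past participant families who have offered to share their experiences in our research studies with potential participants". A reader might infer that this trial's unblinded families are used as contacts for children about to enrol. The text does not say so. It describes an existing network from the laboratory's studies and is silent on whether this trial's families join it. The point does not rest on the network, and there is no case for restricting what the network may discuss: the protocol lists it among its support measures for a vulnerable paediatric population.
- **Trial-end reading of 11.4.** If hand results are given out only when the trial ends, no later child can hear of them. That removes early circulation of individual results. It does not remove the conflict with 7.1 or the per-child unblinding in 5.2.
- **What one family can know.** A family holds one arm and at most one before-after change, in a child who also practised the task during stimulation. That cannot show which arm worked. A later child's own allocation stays concealed.
- **Other sources of expectation.** The symptom questionnaires ask every child about tingling, itching and headache, so families are not the only route to that idea.
- **What families are told.** The closing text of 11.4 reads like participant-facing wording, and the consent pages are not available for review. One cannot conclude that families are given an untrue statement, only that the protocol contradicts itself.
- **Reach.** The intent-to-treat analysis in section 15.3 is of MEP, which expectation should affect little.

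What survives is the unblinding rule, the absence of any safeguard, and the contradiction.

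**Conclusion.** The point holds in limited form. The contradiction between 7.1 and 11.4 is certain. Rolling unblinding is the natural reading of 5.2, supported by three parallel uses of completion in the protocol, though the sentence does not say so outright. It follows that an arm may be disclosed before the child's own adverse-event call.

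The consequence is a modest, avoidable weakening of blinding for task time, Box and Blocks, grip strength and symptom reports, with little bearing on MEP. It assumes that some families talk to others or let knowledge of the arm colour what they report; the documents neither establish nor prevent this.

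A reader might want a figure for the bias. The documents give no share of children who would hear of an arm, no accuracy of guessing and no expectancy effect, so any figure would only restate chosen assumptions. The case for change rests on the gap in the rule and the low cost of closing it.

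**What to change.** 1. **Section 5.2.** State that no arm is released to a participant or family, except for safety need, until the last participant has completed all assessments and the follow-up call, or until database lock. If database lock is chosen, define it, since the protocol does not mention one.
2. **Sections 7.1 and 11.4.** Make these one rule. Either delete the promise in 11.4 and keep the lay summary, or amend 7.1 to allow individual hand results. If results are to be given, release them no earlier than the point set in 5.2, and say that this is a trial-level milestone.
3. **Confidentiality.** Ask any family that learns its arm earlier not to disclose it while the trial is running.
4. **Participant text.** Align the matching wording given to families.

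The cost is wording in three sections and the participant text. Sample size, procedures and analysis do not change. The real downside is that families wait longer for their arm and any results, in the worst case for about the whole 24-month enrolment period plus the last child's follow-up.

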12.0 Withdrawal of Participants

12.1 **Withdrawal Circumstances:** Participants will be withdrawn from the study under any of the following scenarios:

Death: Study stopped for both individual and entire trial. Full investigation of event explored by entire study team. Medical monitor to review all details. Report of event will be distributed to all governing and monitoring committees.

Seizure—Individual: If at any time during the study procedures a participant experiences a seizure, testing will be immediately suspended for that individual and the study team will follow seizure management guidelines. Refer to comprehensive seizure management outline (Appendix J) and the complete seizure observation documentation form (Appendix K). A letter from the Study Physician will be sent to the participant. (Appendix L). The medical director will recommend further evaluation of the child by pediatric neurologist or pediatrician routinely involved in the child's care.

An identification of causality and re-evaluation of treatment design will be performed by study researchers, including consultants, medical monitor and physicians in order to proceed. All procedures will be assessed for strict adherence to all intervention steps listed in the protocol. If deviation is found, the error will be corrected.

Seizure—Multiple: If more than one individual experiences a seizure during the participation in the study, the entire study will be stopped and a thorough review performed by the research team and medical monitor. If a change in protocol is deemed necessary for the safety of participants, an amendment will be submitted to the IRB.

12.2 **Withdrawal Procedures:** If a participant voluntarily withdraws, we will ask the participant if we can continue to use information collected from any data collected up until that point. They will have the option to re-enroll at a later time if desired.

12.3 **Termination Procedures:** If a participant is removed from the study by one of the investigators, any data collected up until the point of termination will be used after termination.

13.0 Risks to Participants

All research procedures will be performed by experienced personnel who have completed required training, including human participants, HIPAA, and CMRR training.

13.1 **Foreseeable Risks:** The tables below outline the anticipated risks associated with tDCS, TMS, and MRI, our plan to mitigate each risk, and the probability of each risk (Improbable--No reported cases, unlikely (few reported cases), likely (many reported cases). Most risks are reversible with proper medical care/treatment, however there is less information on this aspect of risk mitigation.

Risks Associated with Transcranial Direct Current Stimulation (tDCS)		
Anticipated Risks	Risk Mitigation	Probability of Risk
Burn- Electrolysis	Ensure proper electrode contact with skin	Unlikely
Stimulation in participants with reduced sensation	Assess sensation, avoid placing electrodes over areas of decreased sensation	Unlikely
Stimulation over broken skin, reduced resistance	Assess skin integrity, avoid placement of electrodes over recent shaving, skin defects	Unlikely
Stimulation over conductive implants	Screen appropriately for exclusion criteria of implants	Improbable
Stimulation over a tumor which may alter metabolic activity	Screen appropriately for exclusion criteria of neoplasm.	Improbable
Threshold altering pharmacologic agent	Physician review of each medical record for determination of appropriateness for study inclusion.	Improbable/Unknown
Itching, Tingling, Burning Sensation	Ensure proper contact of surface electrodes with skin. Maintain	Likely

in the area of the electrodes	current dosage within low-range of researched dosages. Ensure that electrode sponges are properly sanitized and that saline solution is appropriately employed.	
Headache	Ensure that headband securing electrodes is in proper placement, yet not to the level of impingement of scalp area. Maintain current dosage within low range of delivery.	Likely
Pain- Neck, Scalp	Ensure that electrodes are in proper contact with skin and adjust head position as needed for comfort.	Unlikely
Skin Redness	Ensure proper electrode position and proper level of moisture to even stimulation across the electrode	Likely
Fatigue, Sleepiness	Screen for continuous effect at follow-up visit.	Unlikely
Concentration or Mood Changes	Evaluate cognitive status through physician examination and psychometric testing at three time points.	Unlikely

Risks Associated with Transcranial Magnetic Stimulation (TMS)		
Anticipated Risks	Risk Mitigation	Probability of Risk
Stimulation over a tumor which may alter metabolic activity	Screen appropriately for exclusion criteria of neoplasm.	Improbable
Threshold altering pharmacologic agent	Physician review of each medical record for determination of appropriateness for study inclusion.	Improbable
Headache	Screen for continuous effect throughout session through	Likely

	planned and spontaneous inquiry as well as invitation to report discomfort at any time.	
Fatigue, Sleepiness	Screen for continuous effect throughout session through planned and spontaneous inquiry as well as invitation to report discomfort at any time.	Likely
Temporary mild hearing loss due to noise level of equipment	Ear plugs will be inserted before commencement of TMS application.	Unlikely

We will use IRB-approved screening forms provided by the CMRR to screen both participants and caregivers accompanying participants. This screening will occur immediately prior to scanning.

Risks Associated with Magnetic Resonance Imaging (MRI)		
Anticipated Risks	Risk Mitigation	Probability of Risk
Claustrophobia	Screening for history of fear of small spaces, introduction of MRI environment before scanning	Likely
Metal projectiles	Thorough participant and caregiver screening before scan, high-quality safety practices of research team	Unlikely
Interruption of implanted medical devices or dislodging of indwelling metal	Review of medical records, thorough participant and caregiver screening before scan	Improbable
Other physiologic responses (nausea, headache, muscle stiffness)	Emphasize hydration and ensuring rest before scanning	Unlikely
Effects on unborn fetus	Pregnancy screening of females	Improbable
Dizziness following scan (orthostatic response to lying down)	Moving from a supine to sitting position after completion for 1-2 minutes, accompanying child out of the scanner room	Likely
Temporary mild	Use of foam ear plugs to	Unlikely

hearing loss due to scanner noise	reduce noise intensity before scanning	
-----------------------------------	--	--

- 13.2 **Reproduction Risks:** Both TMS and MRI have unknown risk on the fetus. Therefore, any pregnant women will not be allowed to participate.
- 13.3 **Risks to Others:** For parents/guardians accompanying participants in the CMRR, they are subject to some of the risks associated with MRI scanning. Therefore, all individuals accompanying the participant will be screened using CMRR screening tools.

